**Estimand**

CCI

## 1.2. Study Design

Overview of Study Design and Key Features													
Week	0'	4'	8'	12'	20'	26'	28	32'	36'	40	48	52	56'
Visit	1'	2	3'	4'	5'	6'	7'	8	9'	10'	11	12'	13'

The diagram illustrates the study timeline. It starts with 'Visit 1' (Exit-Visit for Study 206713/213744) at Week 0. This is followed by the 'Study Intervention Period' (Visit 1 dose at Week 0, Visit 2 dose at Week 26). The intervention period ends with 'Visit 13' (Follow-up Visit) at Week 56. A '4-Weeks' follow-up period follows Visit 13. Arrows indicate the timing of doses and visits relative to the start of the intervention period.
													

*The Exit-Visit in 206713/213744 will serve as the Baseline Visit (Visit 1) for this study (212895).  **Participants will remain on standard-of-care asthma therapy, which may be adjusted during the study at the discretion of their physician.
													
Design Features	
 
multicentre, single-arm, open-label 12-month extension study
 
52-week treatment period
 
Participants who completed either study 206713 or 213744 will have the opportunity to participate in this study, regardless of which treatment they were previously randomized.
 
The total number of participants enrolled in this trial will not be greater than the combined number randomised into Studies 206713 and 213744.
 
Participants meeting all the inclusion criteria and none of the exclusion criteria will receive their first open-label dose of GSK3511294 SC at Visit 1 (baseline visit). Participants will receive a second open-label dose of GSK3511294 SC at 26 weeks after Visit 1, providing up to 52 weeks of treatment.
 
												
Study intervention	GSK3511294 100 mg SC												
Study intervention Assignment	All Participants will receive open label GSK3511294 100 mg SC												
Interim Analysis	
 
As the study will be still ongoing at the time of regulatory submission, interim analyses will be performed in order to provide open-label safety and efficacy data in an interim Clinical Study Report (CSR) to inform the risk-benefit assessment of GSK3511294 in asthma with an eosinophilic phenotype.
 
An independent data monitoring committee (IDMC) review of Study 212895 safety data is planned as part of the IDMC review of overall safety for studies 206713 and 213744. Study 212895 is not governed by an IDMC.
 
												

## 2. STATISTICAL HYPOTHESES

Because the study has a single treatment arm, statistical analyses of treatment effect will not be performed. Therefore, no hypotheses have been defined for this study.

### 2.1. Multiplicity Adjustment

This is a single arm study. There will be no treatment comparison. Therefore, multiplicity adjustment is not applicable.

## 3. ANALYSIS SETS

Analysis Set	Definition / Criteria	Analyses Evaluated
Screened	All participants who were screened for eligibility.	
 
• Study Population
 

Enrolled	
All participants who entered the study (who received study intervention or underwent a post screening study procedure).
 
Note screening failures and participants screened but never enrolled into the study (Met eligibility but not needed) are excluded from the Enrolled analysis set as they did not enter the study.
	
 
• Study Population
 

Safety	All participants who receive at least one dose of open-label GSK3511294 excluding participants from sites 250190, 250085 and 250523	
 
• Study Population
 
• Safety
 
• Efficacy
 
• Immunogenicity
 
• PD
 

Safety-Japan	All participants in the Safety population who are enrolled from Japan and with Japanese heritage only	
 
• Study Population
 
• Safety
 
• Efficacy
 
• Immunogenicity
 
• PD
 

Safety-Non-Japan	All participants in the Safety population who are not in Safety-Japan analysis set	
 
• PD
 

Safety-Modified	All participants in the Safety population plus enrolled participants from sites 250190, 250085 and 250523 who received at least one dose of study intervention.	
 
• Key Safety
 

## 4. STATISTICAL ANALYSES

### 4.1. General Considerations

#### 4.1.1. General Methodology

The Safety Analysis Set will be used for all Study Population, Efficacy, Safety, Immunogenicity and PD analyses, unless otherwise stated. The Output and Programming Specification (OPS) document will provide more details.

Confidence intervals will use 95% confidence levels unless otherwise specified.

Unless otherwise specified, continuous data will be summarised using descriptive statistics: n, mean, standard deviation (std), median, minimum and maximum. Categorical data will be summarised as the number and percentage of participants in each category.

A subset of Study Population, Efficacy, Safety, Immunogenicity and PD outputs will be produced for Safety-Japan (and Safety-Non-Japan) analysis sets. A list of these outputs will be included in the OPS.

Additional output(s) will be produced for Safety-Modified analysis set, see OPS for details.

#### 4.1.2. Baseline Definition

For participants whose Exit Visit in 206713 or 213744 was on the same day, or within 7 days of Visit 1 in this study (212895), the assessments collected at Exit Visit in 206713 or 213744 will be copied over to this study's database at the time of reporting. These assessments will be labelled as a subject's baseline values. For participants whose Visit 1 in this study is performed greater than 7 days after the Exit Visit in 206713 or 213744, the assessments will be performed pre-dose at Visit 1 in this study and will be used as baseline values. For participants whose assessments are done at both Exit Visit in 206713 or 213744 and Visit 1, the assessments performed pre-dose at Visit 1 in this study will be used as baseline values. The assessments refer to ECG, vital signs, laboratory, immunogenicity, complement C3 and C4, spirometry, ACQ-5, SGRQ and PGI-S assessments.

Generally, change from baseline will be defined as the difference between the value of the endpoint at the time point of interest and the baseline value. However, if stated below, a change from baseline analysis may be performed on the ratio scale and change from baseline will be the ratio: time point of interest value/baseline value.

#### 4.1.3. Multicentre Studies

The following regions are defined:

- Europe (Czechia, France, Italy, Poland, Spain, UK, Germany, Hungary, Ireland)
- US

- Rest of World (Japan, China, Taiwan, Australia, Canada)

If there are insufficient subjects in each region for the statistical procedures to converge satisfactorily, the combining of regions will be considered.

## 4.2. Primary Endpoint(s) Analyses

The primary endpoints are incidence of AEs/SAEs and incidence of immunogenicity measured by the presence of ADA/NAb to GSK3511294 over 52 weeks. The estimands for the primary endpoints are provided in Section 1.1.

The main analysis approach for incidence of AEs/SAEs is described in Section 4.5.2 while the analysis approach for incidence of immunogenicity measured by the presence of ADA/NAb to GSK3511294 is described in Section 4.6.

## 4.3. Secondary Endpoint(s) Analyses

### 4.3.1. Secondary endpoint(s)

#### 4.3.1.1. Definition of endpoints

The secondary endpoints are:

- Annualized rate of clinically significant exacerbations over 52 weeks
- Change from baseline in ACQ-5 score at discrete timepoints during 52-week period
- Change from baseline in SGRQ total score at Week 26 and Week 52
- Change from baseline in pre-bronchodilator FEV1 at Week 26 and Week 52

#### 4.3.1.2. Main analytical approach

Secondary Endpoints Analyses
Endpoint(s)

 
• Annualized rate of clinically significant exacerbations over 52 weeks
 

Model Specification

 
• Generalized linear model assuming a negative binomial distribution
 
• Terms in the model: 
 
• Response: number of recorded clinically significant exacerbations experienced per subject.
 
• Categorical: treatment group during study 206713 or 213744 and geographical region
 
• Continuous: % predicted pre-bronchodilator FEV1 from the baseline measurement of 206713 or 213744
 
• Offset: Loge(total time in this study in years)
 
 
 

Model Checking & Diagnostics

 
• The fit of the regression models will be examined using “Q-Q” plots of the standardized residuals. Interpretation of these plots will be aided by the addition of simulation-generated tolerance boundaries.
 

Results Presentation

 
• model estimated annualized exacerbation rates and associated 95% CI for: 
 
◦ open-label GSK3511294
 
 
 

Secondary Endpoints Analyses	
○ open-label GSK3511294 and on GSK3511294 in previous study	○ open-label GSK3511294 and on placebo in previous study
Handling of missing data and data excluded due to intercurrent events	
• For participants that discontinue study intervention due to reasons related to the COVID-19 pandemic, CCI	
• For participants that withdraw from the study, preventing assessment of the endpoint, CCI	

Secondary Endpoints Analyses	
Endpoint(s)	
• Change from baseline in SGRQ total score at Week 26 and Week 52	
• Change from baseline in ACQ-5 score at discrete timepoints during the 52-week period	
• Change from baseline in pre-bronchodilator FEV 1 at Week 26 and Week 52	
Model Specification	
• Mixed Models Repeated Measures (MMRM) model.	
• Terms in the model:	
Response: Change from baseline in SGRQ Total score or Change from baseline in ACQ-5 score or Change from baseline in pre-bronchodilator FEV1 at each visit.	
Categorical: treatment group during 206713 or 213744, geographical region, and visit	
Continuous: baseline (SGRQ Total score, or ACQ-5 score, or pre-bronchodilator FEV1), and % predicted pre-bronchodilator FEV1 from the baseline measurement of 206713 or 213744 (for SGRQ total score and ACQ-5 score endpoints only)	
Interaction: treatment group*visit	
Repeated: visit	
• The MMRM analysis for SGRQ total scores will include data collected at Weeks 26 and 52. The MMRM analysis for ACQ-5 score will include data collected at Weeks 4, 8, 12, 20, 24, 26, 28, 32, 40 and 52.	
The MMRM analysis for pre-bronchodilator FEV 1 will include data collected at Weeks 26 and 52.	
• The model will be fit with an unstructured variance-covariance matrix.	
• The Kenward and Roger method (KR) for approximating the denominator degrees of freedom and correcting for bias in the estimated variance-covariance of the fixed effects will be used. In the event the model fails to run using the KR method, then the residual method will be used instead. In the event the model fails to run using residual method and assessments are from many timepoints, timepoints included in the analysis may be reduced by keeping the timepoints/intervals of most interest.	
• Baseline is defined in Section 4.1.2 .	
Model Checking & Diagnostics	
• The fit of the regression models will be examined using “Q-Q” plots of the standardized residuals.	
Results Presentation	
• Least-square (LS) mean change from baseline values will be presented with their associated standard errors as well as 95% CIs for:	
○ open-label GSK3511294	
○ open-label GSK3511294 and on GSK3511294 in previous study	
○ open-label GSK3511294 and on placebo in previous study	

Secondary Endpoints Analyses

• The LS mean and associated 95% CIs for all visits will also be presented graphically.

• SGRQ total scores, ACQ-5 score and pre-bronchodilator FEV1 (absolute value and changes from baseline) will also be summarised by treatment group during 206713 or 213744 and visit.

Handling of missing data and data excluded due to intercurrent events

• For participants that discontinue study intervention due to reasons related to the COVID-19 pandemic, CCI [REDACTED] [REDACTED] [REDACTED]

• For participants that withdraw from the study, preventing assessment of CCI [REDACTED] [REDACTED]

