After giving informed consent for this study, eligibility will be assessed. The assessments at this baseline visit will include informed consent, updated medical history and change in smoking status.

Those participants meeting all the inclusion criteria and none of the exclusion criteria will receive their first open-label dose of GSK3511294 SC at Visit 1. Participants will receive a second dose of GSK3511294 SC approximately 26 weeks after Visit 1.

Number of Participants:

This study is an extension of Study 206713 and Study 213744. Participants must complete study 206713 or 213744 prior to entering this study. The maximum number of participants who are potentially eligible to take part in this study is not greater than the total number of participants enrolled in studies 206713 and 213744 (approximately 750 participants).

Intervention Groups and Duration:

[figure not shown]
Eligible participants will be requested to participate in the study for a maximum of 56 weeks (Visit 1 to the Follow-up visit/call, inclusive). There will be a single treatment arm and all participants will receive open-label GSK3511294 100 mg SC at enrolment (Week 0) and at Week 26. The study consists of two phases described below:

- **Intervention Period:** (Duration - 52 weeks). Participants who meet the eligibility criteria will enter the open-label 52-week treatment period and receive GSK3511294 100 mg SC administered via a prefilled safety syringe, at enrolment (Week 0) and at Week 26. The Exit Visit will occur at Week 52. Following enrolment, visits will occur at Week 4 and approximately every 4 weeks (with some exceptions) thereafter with a visit at Week 26 for the administration of the second dose of GSK3511294 100 mg SC.
- **Follow-up Period:** (Duration – 4 weeks). Participants will be contacted 4 weeks after the Exit Visit. A participant will be regarded as having completed the study if they complete the treatment administration and Exit Visit and the Follow up visit/call, 4 weeks after the Exit Visit.

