4.4. End of Study Definition

The end of the study is defined as the date of the last follow-up visit/call for the last participant in the trial.

Participants will be considered to have completed the study if he/she has completed the Exit Visit and the Follow-up visit/call, 4 weeks after the Exit Visit, regardless of whether the second dose of study intervention (at Week 26) was received.

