9.4.3. Secondary Endpoints

| | |
|---|--|
| Treatment | 
open-label GSK3511294 + SoC
 
Results will also be summarised according to treatment group in studies 206713/213744:
 
 • open-label GSK3511294 + SoC and on GSK3511294 + SoC in previous study • open-label GSK3511294 + SoC and on placebo + SoC in previous study |
| Target Patient Population | 
Adult and adolescent participants with severe asthma with an eosinophilic phenotype following the strategy outlined for dealing with the main intercurrent events that are anticipated
 |
| Endpoint | 
Annualized rate of clinically significant exacerbations. Clinically significant exacerbations are defined in Section 8.4.2
 |
| Intercurrent events and strategies | 
The anticipated key intercurrent events and corresponding strategies are:
 
 a) Study intervention discontinuation due to reasons unrelated to the COVID-19 pandemic: [REDACTED] b) Study intervention discontinuation due to reasons related to the COVID-19 |

| | |
|--|--|
| | 
pandemic: CCI [REDACTED] [REDACTED]
 
c) Change in maintenance therapy or use of prohibited medications: CCI [REDACTED] [REDACTED]
 |
| Summary measure | Annualized exacerbation rate and 95% confidence interval (CI) |
| Analysis Method | The primary analysis of the number of clinically significant exacerbations will use a negative binomial model. Covariates included will be region, and treatment group during 206713/213744 with loge(time in study in years) as an offset variable. |
| Handling of missing data and data to be excluded due to intercurrent events | 
a) For participants that discontinue study intervention due to reasons related to the COVID-19 pandemic, CCI [REDACTED] [REDACTED] [REDACTED] [REDACTED].
 
b) For participants that withdraw from the study, preventing assessment of the endpoint, CCI [REDACTED] [REDACTED]
 |

| | |
|----------------------------------|---|
| Treatment | 
 open-label GSK3511294 + SoC 
Results will also be summarised according to treatment group in studies 206713/213744:
 
 open-label GSK3511294 + SoC and on GSK3511294 + SoC in previous study open-label GSK3511294 + SoC and on placebo + SoC in previous study |

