a) Annualized rate of Clinically significant exacerbations over 52 weeks  b) Change from Baseline in Asthma Control Questionnaire-5 (ACQ-5) score at discrete timepoints during the 52-week period  c) Change from Baseline in St. George's Respiratory Questionnaire (SGRQ)	
 
• Study intervention discontinuation due to reasons unrelated to the COVID 19 pandemic: treatment CCI [REDACTED] [REDACTED] This strategy reflects the ITT principle.
 
• Study intervention discontinuation due to reasons related to the COVID-19 pandemic: CCI [REDACTED]
 
	a) Annualised rate of clinically significant exacerbations over 52 weeks  b) Mean Change from Baseline in ACQ-5 score during the 52-weeks period  c) Mean Change from Baseline in SGRQ total score at Week 26 and Week 52

Estimand		

total score at Week 26 and Week 52.
 
d) Change from Baseline in pre-bronchodilator FEV1 at Week 26 and Week 52
	
• Change in maintenance therapy or use of prohibited medications: CCI [REDACTED] [REDACTED] [REDACTED] [REDACTED]
	
d) Mean Change from Baseline in pre-bronchodilator FEV1 at Week 26 and Week 52

Other Objective: To describe the long-term safety profile of GSK3511294 100 mg (SC) every 26 weeks in participants with severe asthma with an eosinophilic phenotype on top of existing asthma therapy over a 12-month open label extension phase
		

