### 6.2.3. Study Day and Reference Dates

The reference date is the study intervention start date and will be used to calculate study day for efficacy measures and baseline characteristics, as well as efficacy durations. It will also be used to calculate study day for safety measures

The study day is calculated as below:

- Assessment Date = Missing → Study Day = Missing
- Assessment Date < Reference Date → Study Day = Assessment Date – Ref Date
- Assessment Date ≥ Reference Date → Study Day = Assessment Date – Ref Date + 1

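### Does an offset of total time in study, which runs to the Week 56 follow-up, distort the 52-week exacerbation rate?

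*SAP*

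**What the plan says.** **Endpoint.** The model table in SAP 4.3.1.2 names the endpoint "Annualized rate of clinically significant exacerbations over 52 weeks". The summary measure in SAP 1.1.2 carries the same period: "Annualised rate of clinically significant exacerbations over 52 weeks".

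**Model.** The response is the "number of recorded clinically significant exacerbations experienced per subject" and the offset is the log of "total time in this study in years". Protocol 9.4.3 describes the model "with loge(time in study in years) as an offset variable". Neither document attaches an end date to the count or to the time.

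**Length of the study.** Protocol 1.1 sets participation at up to 56 weeks, counted from Visit 1 through the follow-up contact. Under Protocol 4.4 a participant completes the study by having "completed the Exit Visit and the Follow-up visit/call, 4 weeks after the Exit Visit".

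**Collection of exacerbations.** The schedules in Protocol 1.3 and in Table 4 of Protocol 10.9 mark exacerbation review at all 12 visits, at follow-up and at the withdrawal visit. Protocol 8.4.2 ends collection at whichever of the Exit, follow-up or withdrawal contacts applies.

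**Time origin.** SAP 6.2.3 makes the first dose the reference date, which "will be used to calculate study day for efficacy measures and baseline characteristics, as well as efficacy durations". It sets the start of the clock but not the end.

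**What cannot be seen.** The intercurrent-event and missing-data rules for this endpoint are partly redacted in both documents. The Output and Programming Specification, to which SAP 4.1.1 and 4.9.1 refer for output details, is not among the documents.

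**The concern.** A 52-week endpoint paired with a denominator that can run to Week 56 suggests that numerator and denominator cover different periods. If exacerbations were counted only to Week 52 while time ran on to Week 56, every completer would add four weeks in which no event could be counted, and the rate would come out too low. If instead both run to Week 56, the table reports a 56-week rate under a 52-week label.

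The endpoint is the first-listed secondary efficacy endpoint. Under SAP 4.9.1 it also enters the interim report meant to inform the risk-benefit assessment, so a rate about 7% too low would be worth preventing.

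**Working it through.** **Inputs.** Exit Visit at Week 52, Day 364, and follow-up at Week 56, Day 392 (Protocol 1.3). Each visit has a ±7-day window. Planned enrolment is 637 (Protocol 9.2). The documents give no exacerbation rate or dispersion, so those values are assumptions below.

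**1. The plan's own figure.** 52 weeks of intervention + 4 weeks of follow-up = 56 weeks. By the other route, the last dose at Week 26 + 30 weeks = 56 weeks, and 392/7 = 56. The stated maximum is reproduced.

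**2. A completer's offset.** To Week 52: 364/365.25 = 0.9966 years. To Week 56: 392/365.25 = 1.0732 years. The share after Week 52 is 28/392 = 7.1%.

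**3. Four ways to pair events and time** (completers, constant rate):

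| Events to | Time to | Factor on the rate | 0.50 per year (assumed) reads |
|---|---|---|---|
| Week 52 | Week 52 | 1 | 0.50 |
| Week 56 | Week 56 | 1 | 0.50 |
| Week 52 | Week 56 | 364/392 = 0.929 (−7.1%) | 0.464 |
| Week 56 | Week 52 | 392/364 = 1.077 (+7.7%) | 0.538 |

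The first row applies the endpoint label to both terms. The second takes response and offset as written. Both are matched and give the same answer. The last two rows apply the label to one term and ignore it for the other in the same table.

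**4. Visit windows.** The mismatch in the third row would vary between individuals. Taking each window at its opposite extremes, the share of a completer's time after the Exit Visit runs from 14/385 = 3.6% to 42/399 = 10.5%. These are limits for one person. Averaged over participants the share stays near 7.1% unless visits are systematically early or late. On a matched reading the windows do not matter, because events and time stop together.

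**5. A changing rate.** If both terms run to Week 56 and the rate in Weeks 52–56 is m times the earlier rate, the result relative to the 52-week rate is (52 + 4m)/56. For assumed m = 0.5, 1.5, 2 and 3 this gives 0.964, 1.036, 1.071 and 1.143.

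**6. Precision for scale.** With SE(log rate) = √[(1/(rate × t) + k)/637] and t = 0.9966, an assumed rate of 1.0 with dispersion k = 0.5 gives SE 0.0486, so the upper 95% limit lies exp(1.96 × 0.0486) − 1 = 10% above the estimate. A rate of 0.3 with k = 1.0 gives SE 0.0826 and 18%.

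**7. Interim cut.** SAP 4.9.1 drops all data after the cut-off date, which truncates events and follow-up together. Participants who have not reached Week 52 contribute no later time.

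**The case for a change.** The best argument for a change is that other quantities in the SAP have explicit end rules while this one has none. Exposure has a formula (SAP 4.5.1), and adverse events have phase definitions ending at last dose + 182 days (SAP 6.2.2.3). Protocol 8.4.2 leaves the end of collection open among three contacts. Events after Week 52 will be in the database, so keeping or dropping them is a real programming decision, and one sentence would settle it. Cutting both terms at Week 52 would cost little: at most 637 × 28/365.25 = 48.8 of 683.7 person-years, with the SE of the log rate rising by 1.8% to 3.3% under assumed rates of 0.3–1.0 and dispersions of 0.5–1.0.

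There is also a point about capture. Footnote i to the schedule gives the purpose of the follow-up contact as adverse-event assessment and pregnancy testing, although the exacerbation row is marked there too. If half the events after Week 52 went unrecorded while the time was counted, the rate would be (52 + 2)/56 = 0.964 of its true value, a loss of 3.6%.

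The end date is indeed not visible, and the 52-week label is inexact if both terms run to follow-up. But two analysts who each keep events and time together will agree at a constant rate whichever end they choose, so the open wording does not by itself produce a 7% disagreement. Incomplete capture at follow-up is a conjecture, since both schedules call for the review. A Week 52 rule written without sight of the redacted text could also clash with the separate handling of participants who stop because of the pandemic.

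**Conclusion.** No change follows. This is missing detail that analysts would fill sensibly. As written, the model divides exacerbations recorded in the study by time in the study. The annualised rate is then unbiased if recording is complete to the last contact and the rate is constant through Week 56. The shifts of −7.1% and +7.7% belong only to mismatched windows that the text does not call for. Even so, they are smaller than the 10% to 18% distance from the estimate to its upper confidence limit under the assumed rates and dispersions.

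A genuine change in rate after Week 52 would move a 56-week figure away from a 52-week one, by −3.6% to +14.3% for the assumed multipliers of 0.5 to 3, but the documents give no reason to expect a particular value. SAP Section 2 states no hypotheses and Section 2.1 rules out treatment comparisons, so no decision rule depends on the estimate. The conclusion is limited to the visible text: a cut-off may already be stated in the redacted rules or in the output specification.

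### The MMRM fixes one baseline slope for all visits, so by-group LS means (chiefly ACQ-5) can be biased if the slope changes over time and the prior-treatment groups differ at baseline

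*SAP*

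**What the plan says.** SAP section 4.3.1.2 specifies an MMRM for change from baseline in SGRQ total score, ACQ-5 score and pre-bronchodilator FEV1. The categorical terms are prior treatment group, region and visit. The endpoint's own baseline is a continuous main effect. The only interaction listed is "treatment group*visit". On covariance the SAP says: "The model will be fit with an unstructured variance-covariance matrix".

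The visits differ by endpoint. For ACQ-5: "The MMRM analysis for ACQ-5 score will include data collected at Weeks 4, 8, 12, 20, 24, 26, 28, 32, 40 and 52". Week 24 is not a visit in the protocol's Schedule of Activities, which leaves nine scheduled visits. For SGRQ: "The MMRM analysis for SGRQ total scores will include data collected at Weeks 26 and 52". FEV1 uses the same two weeks.

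LS mean changes are reported with SEs and 95% CIs, overall and for each prior-treatment group, including "open-label GSK3511294 and on placebo in previous study". They are also plotted for all visits. Alongside these, observed values and changes "will also be summarised by treatment group during 206713 or 213744 and visit".

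Under SAP section 4.1.2, baseline is the parent-study Exit Visit or the pre-dose Visit 1 assessment. Either way it follows 52 weeks of active drug or placebo. The protocol's outline of the model (section 9.4.3) lists no baseline covariate, so it does not settle how the slope should be handled.

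**The concern.** Group-by-visit means are free and the covariance is unstructured, but the relation of change to baseline is forced to be the same at Week 4 as at Week 52. The SAP gives no reason for this.

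In a comparison of freshly randomised arms, such a restriction does little harm because the arms share a baseline mean. Here the reported groups are continuers and new starters, and their baselines come after a year of different treatment. If the parent treatment affected ACQ-5, SGRQ or FEV1, the groups start at different levels. A slope that is wrong at a given visit then moves the two LS means in opposite directions. At stake are the calibration of the by-group 95% CIs and the shape of the plotted time course. The only stated diagnostic for this model, Q-Q plots of residuals, is not designed to detect a slope that varies by visit.

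**Working it through.** **The plan's own figure.** Protocol section 9.2 takes about 750 eligible less 15%: 750 x 0.85 = 637.5, stated as 637. This reproduces and is used as N. The documents state no bias, SE or coverage for the MMRM.

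**Assumptions not in the documents.** Prior-placebo share one third (one half as a check). Residual SD 0.8 of the baseline SD. Baseline slope moving linearly from Week 4 to Week 52, starting at -0.2, with a total change of 0 to 0.4. Gap in mean baseline between groups of 0 to 0.5 SD. LS means evaluated at the pooled baseline mean, because the SAP does not state the evaluation point.

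**Formulas.** With complete data and free group-by-visit means:

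- bias for group g at visit t = (b - beta_t) x (overall mean baseline - group g mean baseline), where b is the common slope and beta_t the true slope at visit t;
- SE is about sqrt(0.8^2 + (b - beta_t)^2) / sqrt(n_g), in baseline-SD units;
- coverage at a bias of k SE = Phi(1.96 - k) - Phi(-1.96 - k).

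**One cell in full.** Slope change 0.3, gap 0.4 SD, prior-placebo share one third. Generalised least squares under an assumed correlated residual structure gave b = -0.338, which is 46% of the way from the Week 4 slope to the Week 52 slope (an unweighted mean over the nine visits would be 43%).

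- Slope error at Week 52: -0.338 - (-0.5) = 0.162.
- Group's distance from the overall mean: 2/3 x 0.4 = 0.267. Bias: 0.162 x 0.267 = 0.043.
- n_g = 637/3 = 212.3. SE: sqrt(0.64 + 0.026)/14.57 = 0.056.
- Ratio: 0.77. Coverage: Phi(1.19) - Phi(-2.73) = 0.88.

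**ACQ-5, nine visits: largest |bias|/SE for the prior-placebo LS mean**

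| Slope change | Gap 0.1 SD | 0.2 SD | 0.3 SD | 0.4 SD |
|---|---|---|---|---|
| 0 | 0 | 0 | 0 | 0 |
| 0.1 | 0.07 | 0.13 | 0.20 | 0.26 |
| 0.2 | 0.13 | 0.26 | 0.39 | 0.52 |
| 0.3 | 0.19 | 0.39 | 0.58 | 0.77 |
| 0.4 | 0.25 | 0.51 | 0.76 | 1.01 |

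An equal split gives values about 8% lower. Coverage is 0.943 at 0.25 SE, 0.921 at 0.5 SE, 0.883 at 0.75 SE and 0.830 at 1 SE.

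**On the ACQ-5 scale.** Take two groups of 318, residual SD 0.8 points, slopes from -0.15 to -0.45 with the common slope about midway, and a gap of 0.4 points. The bias is 0.15 x 0.2 = 0.03 points, against an SE of 0.8/sqrt(318) = 0.045. That is about 0.67 SE, with coverage of about 0.90.

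**SGRQ and FEV1, Weeks 26 and 52.** The common slope lies midway. For a slope change of 0.1 and a gap of 0.4 SD: 0.05 x 0.267 = 0.0133, divided by 0.055, gives 0.24 SE. For 0.05 and 0.1 SD it is 0.03 SE. A slope change of 0.3 with a gap of 0.4 SD would give 0.72 SE.

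**Simulation.** The MMRM was fitted with and without baseline*visit (N = 637, nine visits, dropout missing at random, 200 runs per scenario). Monte Carlo error is about sqrt(0.95 x 0.05/200) = 0.015 on coverage and 1/sqrt(200) = 0.07 on bias/SE.

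| Slope change, gap | Max bias/SE, SAP model | Coverage at Weeks 4 and 52, SAP model |
|---|---|---|
| 0.2, 0.2 SD | 0.37 | 0.94-0.99 |
| 0.3, 0.3 SD | 0.62 | 0.90-0.95 |
| 0.4, 0.4 SD | 0.99 | 0.84-0.92 |

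Bias was largest at the end visits and near zero around Week 26. With baseline*visit added, it was at most 0.16 SE in every scenario, and coverage was 0.92 to 0.98. The exact zero for equal baselines is a complete-data result: with dropout, a slope change of 0.2 and no gap, the largest simulated value under the SAP model was 0.22 SE.

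**The case against.** The strongest reply is that the problem needs two things at once, a drifting slope and a baseline gap, and the documents give neither. That stands: a baseline gap is plausible from the design, but its size is unknown, and nothing in the documents says that the slope changes with time. A reader might infer that the LS means are biased and the intervals wrong. The documents support only that they can be.

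The effect also depends on where the LS means are evaluated. Taken at each group's own baseline mean, the complete-data bias vanishes. The SAP does not state the evaluation point, so the pooled mean remains an assumption.

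The consequences are limited. The endpoints are secondary, no hypothesis is tested, and the observed by-visit summaries carry no slope restriction. In the overall open-label LS mean the group errors cancel if groups are weighted by size. With equal weights and a one-third share, (b - beta_t) x gap/6 would remain, because (2/3 - 1/3)/2 = 1/6. The absolute shift of about 0.03 points is small on the 0 to 6 ACQ-5 scale. All this limits the importance. It does not correct the model-based by-group intervals, whose SE is itself only about 0.045 points.

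**Conclusion.** The point holds as a conditional one. The SAP imposes a common baseline slope without justification, in a design where the reported groups may well differ at baseline.

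Under the assumptions above, ACQ-5 bias at the worst visit is about 0.1 to 0.8 SE for slope changes of 0.1 to 0.3 and gaps of 0.1 to 0.4 SD. Coverage runs from about 0.95 down to 0.88-0.90. At a slope change of 0.4 and a gap of 0.4 SD the bias is about 1 SE, with coverage of about 0.83 to 0.92.

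Two stronger readings should be resisted. One SE is neither a ceiling nor an expected value: a gap of 0.5 SD with a slope change of 0.4 gives 1.27 SE, and milder assumptions give far less. And the long Week 4 to Week 52 span belongs to ACQ-5 only. For SGRQ and FEV1 the figure is about 0.03 to 0.24 SE for slope changes of 0.05 to 0.1.

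This is a minor improvement to the analysis and does not threaten the study's conclusions.

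**What to change.** Add baseline*visit to the MMRM interaction terms in SAP section 4.3.1.2 for ACQ-5, SGRQ total score and pre-bronchodilator FEV1. The cost is 8 extra degrees of freedom for ACQ-5 (nine scheduled visits less one) and 1 each for SGRQ and FEV1, with negligible loss of precision at about 600 participants. No new data, change of estimand or change in conduct is needed. If the sponsor prefers a common slope, the SAP should say why.
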